We plan to conduct an open-label, single-center, single-arm three-period study. We aim to recruit 25 adolescents aged 13-18 years with poorly controlled T1D as evidenced by Hemoglobin A1c \geq 12% or a 30% annual risk of developing DKA in the following year according to a predictive model developed at our institution. At a threshold value of probability of admission \geq 0.3 (95% specificity) our model can identify a high-risk subset of approximately 8% of the patients who collectively have a 40% probability of admission in the 12 months following assessment.⁸ We will obtain a written informed consent from guardians and assent from study participants before any study-related activities. We will obtain each patient's demographic information, time since diagnosis, previous hospital admissions. Patient Health Questionnaire (PHQ-9A)⁹ and a point-of-care hemoglobin A1c as standard of care. We will administer a quality of life questionnaire (assessed by the Pediatric Quality Life Inventory for teens 13-18, PedsQL4.0)¹⁰, a self-efficacy and self-management questionnaire (assessed by The Self-Efficacy for Diabetes Self-Management measure (SEDM)¹⁰), and a questionnaire to assess parent-child collaboration in diabetes care (assessed by the Collaborative Parent Involvement Scale¹²).

The first phase of the study will be a surveillance phase in which a blinded Dexcom G6 will be used to obtain baseline values including time in range, percent highs, and percent lows, and percent CGM use. We will use this phase as a run-in period to reduce the chance of noncompliance with the study.

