- Willing to wear CGM and utilize the share function to clinician and guardian, with measuring blood glucose checks as required by the CGM.
- Owning a smartphone compatible with Dexcom G6 software to allow the use of share/follow features with internet access capabilities
- Willing to participate in secure text messaging with study personnel.
- Female participants must have a negative pregnancy test.

Exclusion criteria

- Type 2 diabetes, secondary diabetes or CF related diabetes.
- Other severe chronic disease (e.g., cancer) which in the judgment of the investigator is likely to significantly affect glycemic control.
- Patients cannot be taking systemic corticosteroids at enrollment because of adverse effects on glycemic control, but we will not disqualify subjects who require such therapy during the study. Inhaled or topical corticosteroids are permissible.
- Patients with uncontrolled hypothyroidism (TSH >20) or uncontrolled hyperthyroidism will be excluded from the study. Patients with out of range values may be retested after medication dose adjustment.

- Developmental delay or behavioral disorder in the patient of sufficient severity, in the judgment of the investigator, to interfere with study activities. Severe uncontrolled depression defined as PHQ-9A >15 at time of enrollment is an exclusion criterion.
- Medical or psychiatric disorder in a parent of sufficient severity, in the judgment of the investigator, to interfere with study activities.
- Pregnancy, planned pregnancy or breast feeding
- CGM adhesive allergy
- Skin condition that makes CGM placement contraindicated.
- Sick cell disease or hemoglobinopathy
- Red blood cell transfusion within 3 months prior to study enrollment

Recruitment

Study team members or clinic providers can distribute flyers to patients who qualify to participate in this research study to aid in recruitment of participants. The patient recruitment flyer contains basic description of the study, including use of Dexcom G6, study timeline, brief descriptions of each visit, and compensation for participating in the study. Please see Appendix 1 for copy of the flyer.

Other forms of recruitment include distributing letters via mail and via Children's Health MyChart web portal to patients who may qualify for the study. Please see Appendix 2 for the template for the letters.

Study Timeline

Study procedures

Study design

This is a pilot study that will not include a control group. It will enroll 25 subjects.

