Collaborative Parent Involvement Scale		X		X	X

[figure not shown]

Figure 1. Timeline for study. Study visits are denoted by arrows. A timescale in months is below the timeline; there is not a specified interval between Visits 1 & 2.

Participant withdrawal criteria

The following study withdrawal criteria will apply:

1. Participants can terminate involvement in the study at any time point without any repercussions.
2. If data on the CGM is available < 60% of the time worn, patient may be withdrawn at the discretion of the research investigator.
3. If pregnancy occurs during study period.
4. Allergic reaction to adhesive surface of CGM sensor

Primary endpoint

The primary outcome is change in Hemoglobin A1c (HbA1c) between the baseline visit (Visit 2) and three-month follow-up visit (Visit 3) after active remote monitoring and secure text messaging.

A 5% significance level will be used to declare statistical significance for the primary outcome comparison.

Exploratory endpoints

- Change in Peds PHQ-9A, PED-QOL4A, SEDM, and Collaborative Parent Involvement Scale scores.
- Time taken for a text to be read by participant and guardian.
- Time spent by medical provider per participant per day.
- The difference in A1c between clinical remote monitoring HbA1c (Visit 3) and self-monitoring utilizing CGM (Visit 4)
- The difference in A1c from baseline (Visit 2) and after the two phases of the study intervention (Visit 4).
- The following outcomes will be compared between baseline, three months and six months using repeated measures ANOVA as follows:
 - Time spent in the target glucose range from 70–180 mg/dL
 - Time spent below target glucose 70 mg/dL

- Time spent above target glucose 180 mg/dL
- Average of time the participants wore the CGM

Statistical Plan

Paired sample t-tests will be used to assess continuous variable differences between two time points. Generalized linear models will be run to identify items in medical and social histories that could predict hemoglobin A1c, the primary outcome. Point estimates will be reported with 95% CIs.

As this is a pilot exploratory study, we will implement per-protocol analysis and not an intention-to-treat analysis. Only patients who have completed the three phases of the study will be included for analysis.

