Utilizing a standard deviation of HbA1c of 1.5%, a sample size of 18 participants will be required to detect a 1% change in HbA1c between the baseline measurement and 3-month measurement, assuming an alpha of 0.05 and a beta of 0.20 (80% power).

Safety endpoints

The following safety outcomes will be tabulated by treatment group:

- Number of subjects with any DKA events requiring hospitalization
- Number of subjects with any severe hypoglycemic or hyperglycemic events requiring an emergency room visit or hospitalization
- Number of episodes of moderate to large ketones managed in an outpatient basis

All adverse events will be listed for the entire study duration.

Data management

Dexcom Clarity reports will be used to obtain aggregate 90-day data regarding CGM parameters including average glucose with standard deviation, time in range, percent highs, percent lows, severe lows, and percent days with CGM data (this will be used to compare data across Visits 2T and Visit 4). Additionally, we will collect above data points retrospectively week-by-week for secondary analysis to evaluate progress over time.

Confidentiality of participant data will be observed during the study. Electronic data will be stored in secure password protected computers, and all paper records will be stored in locked researcher's offices. Anonymous data could be shared with third parties to advance diabetes treatment and for study publication purposes.

Protections Against Risk

Confidentiality

Privacy of Personal Data

The collection and processing of personal data from subjects enrolled in this study will be limited to those data that are necessary to fulfill the objectives of the study. These data will be collected and processed with adequate precautions to ensure confidentiality and compliance with applicable data privacy protection laws and regulations. Electronic data will be stored on secure servers that require password protection and maintain audit records of access, and/or on laptops with password-protected encrypted hard drives. All data sent between institutions via e-mail, file transfer protocols or physical media must be encrypted and password protected. Sponsor personnel whose responsibilities require access to personal data agree to keep the identity of study subjects confidential. Hardcopy documentation must be stored in locked file cabinets or locked offices secured with either key or badge access.

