The informed consent and HIPAA permission obtained from the subject's legally acceptable representative includes explicit consent for the processing of personal data and for the investigator to allow direct access to his or her original medical records for study-related monitoring, audit, IRB review, and regulatory inspection. This consent also addresses the transfer of the data to other entities and to other countries.

For any telemedicine visits completed, verbal consent to perform a telemedicine visit will be obtained from the participant's parent/legal guardian/legal representative. All telemedicine visits will be completed using Children's Health telemedicine platform.

The subject's legally acceptable representative has the right to request through the investigator access to the subject's personal data and the right to request rectification of any data that are not correct or complete. Reasonable steps will be taken to respond to such a request, taking into consideration the nature of the request, the conditions of the study, and the applicable laws and regulations.

Disclosure to outside entities

All data, whether electronic or hardcopy, will be referenced to a unique patient identifier, with subjects' identifying information kept in separate secure files. The following entities will be granted access to some or all data and specimens from this study:

- The UT Southwestern Institutional Review Board (IRB).
- Dexcom, Inc.
- Representatives of other governmental and regulatory agencies.

Data and Safety Monitoring Plan

This study represents minimal incremental risk over routine care for children with type 1 diabetes. Accordingly, a separate DSMB is not indicated.

ClinicalTrials.gov

We will register the study with ClinicalTrials.gov prior to enrolling any subjects.

Adverse event reporting

No investigational drug or device will be used in these studies, and consequently adverse event reporting, *per se*, is not applicable. However, we will monitor as secondary outcomes hypoglycemia frequency, DKA admission risk, and report all study adverse events.

Budget: \$37,300 (Dexcom, Inc will provide the CGM devices for the study)

Certified Diabetes Educator time - 36 hours per week \times 20 weeks of study \times \$50 per hour = \$36,000

iPad devices for monitoring CGM data – 2 devices \times \$350 per iPad _____ = \$700

Patient incentive gift cards – \$10 \times 3 visits \times 25 participants) _____ = \$600

[figure not shown]

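### Safety tables are laid out by treatment groups that a single-arm study does not have, and the completers-only rule, which makes no exception for safety, could leave early leavers out of them

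*Combined protocol and SAP*

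**What the plan says.** The Overview of methodology describes the design: "We plan to conduct an open-label, single-center, single-arm three-period study". Study design adds: "This is a pilot study that will not include a control group". The periods are a blinded CGM run-in, a period of unblinded CGM with real-time clinic monitoring and texting, and a period of unblinded CGM without that monitoring.

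Safety endpoints nevertheless opens with: "The following safety outcomes will be tabulated by treatment group". Three outcomes follow. Two count subjects, for example "Number of subjects with any DKA events requiring hospitalization". The third counts episodes of moderate to large ketones managed as an outpatient. No denominator, observation period or breakdown by phase is given.

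The only analysis population is in the Statistical Plan, which says that "we will implement per-protocol analysis and not an intention-to-treat analysis" and then: "Only patients who have completed the three phases of the study will be included for analysis". No safety population is defined.

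Two statements are not limited to completers. Safety endpoints ends with: "All adverse events will be listed for the entire study duration". Adverse event reporting says: "we will monitor as secondary outcomes hypoglycemia frequency, DKA admission risk, and report all study adverse events".

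**The concern.** There are two problems. The first is layout. With one arm, the instruction on how to split the tables cannot be followed. The only natural split is by phase, and the plan does not choose it or say how phases of very different length would be compared.

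The second is who is counted. The completers-only sentence is general, and the safety tables come shortly after it with no population of their own. Followed literally, it removes from the tables anyone who leaves before Visit 4, whatever happened to them first. If leaving is related to having an event, the tabulated risk is too low.

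This matters because participants are selected for high DKA risk or very high HbA1c, staff give insulin-dosing recommendations by text in the monitored phase, and no separate DSMB is planned. The safety tables would be the main summary of harm for anyone deciding whether to extend the approach.

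**Working it through.** **The plan's own figure.** The documents give no safety figure to reproduce. The one sample-size figure, 18, does reproduce if 1.5% is read as the SD of the paired change: (1.5 × (1.960 + 0.842) / 1)² = 17.66, rounded up to 18. It concerns HbA1c and does not bear on this point.

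**Phase lengths.**
- Run-in: the call is at 10 days (+4). If home set-up fails, Visit 2B follows within 5 days. Range: 10 to 10 + 4 + 5 = 19 days.
- Monitored and unmonitored phases: Visit 3 falls 11 to 12 weeks (±5 days) after Visit 2T or 2B, and Visit 4 the same interval after Visit 3. Range for each: 77 − 5 = 72 to 84 + 5 = 89 days.
- Ratio of a later phase to the run-in: 72/19 = 3.8 to 89/10 = 8.9.

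**What unequal length does to counts.** Assume that the 40% 12-month admission probability given for the model's high-risk subset applies to all 25 participants at a constant hazard. The expected number admitted in a period of d days is 25 × (1 − 0.6^(d/365)):
- run-in: 0.35 (10 days) to 0.66 (19 days);
- each later phase: 2.4 (72 days) to 2.9 (89 days).

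The underlying rate is identical throughout, yet the later phases show several times as many affected subjects. Raw counts by phase would look like a change in risk where there is none.

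**How many events to expect overall.** The stated participation time is 6 to 7 months. With m in months, the expected number of participants with an admission is 25 × (1 − (1 − p)^(m/12)):
- p = 0.30 (the entry threshold): 4.1 to 4.7;
- p = 0.40: 5.6 to 6.4.

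A figure of 6 among 25 is therefore a reasonable illustration, though not a forecast.

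**What the completers-only rule could do to that figure.** Suppose that 6 of 25 have an event and that only participants with an event leave. Intervals are exact 95% (Clopper-Pearson).

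| Leavers after an event | Completers table | 95% CI |
|---|---|---|
| 0 | 6/25 = 24% | 9% to 45% |
| 3 | 3/22 = 13.6% | 3% to 35% |
| 6 | 0/19 = 0% | 0% to 18% |

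The last row is the extreme. Where a real study would fall between the first and last rows depends on who leaves, and the documents do not say.

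**The case against.** The strongest reply is that the completers-only sentence was never meant for safety. It sits under Statistical Plan beside the paired t-tests, the HbA1c models and the choice against intention-to-treat, and the HbA1c sample size follows it directly. Safety endpoints is a separate heading with its own commitment to list every adverse event, and Adverse event reporting repeats the commitment to report them all. With 25 participants, a reader could count the events from a listing. DKA is not a withdrawal criterion, so nothing shows that those who have it will leave.

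Much of this stands. A reader might infer that the plan conceals events in dropouts. It does not: those events would be listed, and no sentence says outright that the safety tables omit them. But a listing carries no denominator, person-time or comparison between phases, and the completers-only sentence has no qualifier confining it to efficacy. Two analysts could produce different tables from this text.

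A reader might also infer a definite loss by taking 25 − 18 = 7 as the expected number of dropouts. The documents state no dropout rate, so that is an assumption. Using the 40% risk over 168 days, 7 × (1 − 0.6^(168/365)) gives about 1.5 missing cases, but only if all seven are at risk for the full 24 weeks. With departures spread evenly over the 168 days the figure is about 0.8. If all seven leave at day 14, a planned decision point on CGM wear, it is about 0.14. The 40% figure also belongs to the model-selected subset, and no admission risk is given for those who enter on HbA1c alone.

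Finally, a reader might conclude that it is these defects that stop the tables showing the risk of the intervention. Without a control group no tabulation could attribute risk to it, and on the assumptions above the run-in, with well under one expected case, would be a weak internal comparator.

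**Conclusion.** The point holds in a limited form. Tabulating by treatment group is incompatible with a single-arm design, on the text alone and without any assumption. The completers-only rule, as written, would drop from the safety tables a participant who has an event and then leaves, so those tables could understate event risk even though the listing would still show the event. The direction of the bias assumes that leaving is linked to having an event; its size cannot be fixed from the documents. The range from 24% to 0% is illustrative and rests on an assumed 6 events. The difference in phase length, roughly 4-fold to 9-fold, comes directly from the visit windows and makes raw counts by phase non-comparable.

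The sponsor should correct this. The change is one of wording and table layout, and it does not call the design into question.

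**What to change.** In Safety endpoints, replace the reference to treatment group with: by study phase and overall, in all enrolled participants from Visit 2 until Visit 4 or withdrawal. For each phase and overall, report the number of subjects with an event, the number of events and the person-days at risk. State in the Statistical Plan that the completers-only rule does not apply to safety. Describe the tables as descriptive.

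The cost is a revised table shell and a few sentences. There is one limitation to record. Adverse events are reviewed at Visits 3 and 4 and no early-termination visit is described, so events in participants who leave before Visit 3 would be counted only up to withdrawal, from data already available.

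### Severe hypoglycaemia has no row of its own in the safety table, so that table alone could not show a rise in severe lows if severe highs fell

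*Combined protocol and SAP*

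**What the plan says.** The Safety endpoints section lists three outcomes for tabulation:

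- Row 1: "Number of subjects with any DKA events requiring hospitalization".
- Row 2: "Number of subjects with any severe hypoglycemic or hyperglycemic events requiring an emergency room visit or hospitalization".
- Row 3: "Number of episodes of moderate to large ketones managed in an outpatient basis".

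The lead-in is "The following safety outcomes will be tabulated by treatment group", although Study design states: "This is a pilot study that will not include a control group. It will enroll 25 subjects". The same section adds that every adverse event over the whole study will be listed, with no limit by care setting.

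Hypoglycaemia also appears in three other places. Exploratory endpoints includes "Time spent below target glucose 70 mg/dL", compared at baseline, three months and six months. Data management takes from the Clarity reports "time in range, percent highs, percent lows, severe lows, and percent days with CGM data", for comparison across Visits 2T and 4 and for a week-by-week secondary analysis. Adverse event reporting says that "we will monitor as secondary outcomes hypoglycemia frequency, DKA admission risk, and report all study adverse events". The document defines neither severe events nor hypoglycaemia frequency.

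**The concern.** During the monitored phase, staff advise on insulin by text and review trends weekly; one sample message suggests a carbohydrate ratio that gives more insulin. Fewer severe highs is the hoped-for result. More severe lows is a harm that a safety table should be able to show. A participant-level count of either event cannot do so if the two move in opposite directions, and a participant who has both counts once.

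Coverage is also uneven. High-side events have row 1, row 3 and a share of row 2; low-side events have only a share of row 2. The plan accepts, through row 3, that events handled outside hospital matter, but gives lows no matching row. The emergency-or-hospital limit could also work differently by phase. In the monitored phase staff text about qualifying lows and call the guardian or school if there is no reply in 30 minutes; after Visit 3 this stops.

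The Background says the study will assess safety. What is at stake is whether its safety table can answer the question about severe lows.

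**Working it through.** **Inputs.** Row definitions come from Safety endpoints, 25 participants from Study design, and phase lengths from the visit schedule. The plan gives no rate for severe hypoglycaemia or hyperglycaemia, so every rate below is an assumption. No figure is attached to the safety rows. The plan's only calculated figure, 18 participants, concerns HbA1c: (1.5 × 2.8016 / 1)² = 17.66, rounded up to 18, reading 1.5% as the SD of the change. It reproduces, and nothing here alters it.

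**Step 1: where each event would be tabulated.**

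| Event | Tabulated in |
|---|---|
| DKA, hospitalized | Row 1; nothing excludes it from row 2 |
| Other severe high, emergency or hospital | Row 2, with lows |
| Moderate to large ketones, outpatient | Row 3 |
| Severe low, emergency or hospital | Row 2, with highs |
| Severe low, managed elsewhere | No row (adverse event listing and CGM measures only) |

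**Step 2: what row 2 can show.** Let a be a participant's risk of a severe low and b that of a severe high, taken as independent. The row-2 probability is 1 − (1 − a)(1 − b).

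| Assumed a, b | Row-2 probability | Row 2, of 25 | With a severe low, of 25 |
|---|---|---|---|
| 4%, 20% | 1 − 0.96 × 0.80 = 23.2% | 5.8 | 1 |
| 12%, 12% | 1 − 0.88 × 0.88 = 22.6% | 5.6 | 3 |
| 20%, 4% | 1 − 0.80 × 0.96 = 23.2% | 5.8 | 5 |

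The row barely moves while severe lows rise fivefold. In simple counts of different participants, 4 highs and 0 lows give 4, and so do 1 high and 3 lows.

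**Step 3: exposure by phase.** The blinded phase ends with a call at 10 days (up to 14 with the window). Each later phase is 11–12 weeks, or 77–84 days. Against 10 days the ratio is 77/10 = 7.7 to 84/10 = 8.4; against 14 days it is 77/14 = 5.5 to 84/14 = 6.0. At a constant event rate a later phase would show roughly 5.5 to 8.4 times as many episodes, ignoring the ±5-day visit windows. Raw counts by phase would therefore mislead even after a split.

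**Step 4: the promise set against the endpoint lists.** Hypoglycaemia frequency is called a secondary outcome, but the document lists only primary, exploratory and safety endpoints, and none is a frequency of hypoglycaemia. Time below 70 mg/dL is a duration and does not isolate severe lows. Clarity severe lows are collected but named in no endpoint list. Their stated aggregate comparison runs across Visits 2T and 4 and does not name Visit 3, where the monitored phase ends. The figure for that phase should still exist, because CGM reports are analysed at Visit 3 and weekly values are collected.

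**The case against.** The strongest reply is that hypoglycaemia is observed in several ways outside row 2. All adverse events are listed without a care-setting limit and are reviewed at Visits 3 and 4; with 25 participants a reader can separate lows from highs in a listing. CGM time below 70 mg/dL is compared at three time points, and Clarity severe lows are compared and followed weekly, unpooled and whatever the care setting.

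Much of this stands, and it rules out three stronger readings that a reader might infer:

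- **Severe lows treated at home are never counted.** Not supported, given the listing and the CGM measures. They have no tabulated event count.
- **Harm will be cancelled by benefit.** Not supported. The study has one arm and no between-phase safety comparison is specified. The direction of change is also unknown: the intervention targets lows too, with mandatory alarms below 70 mg/dL and mandatory texts. Nor do the documents show that the care-setting limit would distort phase counts; that is a possibility.
- **DKA admissions are double-counted.** Not supported. Rows 1 and 2 can overlap but are never summed. The overlap only makes row 2 harder to interpret.

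What the reply does not remove is the gap in tabulation. A listing is not a summary, and Adverse event reporting weakens it by saying that such reporting does not strictly apply. CGM lows are not the same thing as clinically severe events.

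**Conclusion.** The point holds as a gap in the tabulated safety endpoints. Severe hypoglycaemia has no separate count, lows managed outside emergency or hospital care have no row, and the promised hypoglycaemia frequency is tied to no endpoint. Row 2 alone could stay near 23% while expected participants with severe lows rose from 1 to 5 of 25. That rests on assumed rates, independence and an equal opposite fall in highs, so it shows what the row can hide and not what will happen. The documents do not give the share of severe lows managed outside hospital, so the number missed by the care-setting limit cannot be estimated.

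The primary endpoint and sample size are untouched and the underlying data are largely collected. The change is worth making because it is nearly free and lets the safety table answer a question that the study raises.

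**What to change.** 1. Split row 2 into (a) severe hypoglycaemia and (b) severe hyperglycaemia other than DKA admissions already in row 1.
2. For (a), report participants and episodes wherever managed, with the emergency or hospital subset shown. The investigators should fix a definition of severe before analysis; without the care-setting limit there is no other working criterion.
3. Replace tabulation by treatment group with tabulation by study phase, and show exposure time for each phase.
4. Name the Clarity severe-lows figure as a safety outcome for each phase, including the monitored phase ending at Visit 3, and state which measure delivers the promised hypoglycaemia frequency.

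Cost: protocol wording, one more table row, and a question about home-managed episodes at the adverse event reviews at Visits 3 and 4. No such review is described for the Visit 2B/2T contact, so blinded-phase episodes would have to be asked about there or recalled at Visit 3. The downside is that home-managed episodes are partly self-reported and are found more readily when staff are watching and texts are stored. The report should disclose that ascertainment differs between monitored and unmonitored phases. Sample size and treatment do not change.
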